e. If children are included in the study, if and how you will obtain assent from them:

All enrolled participants will be legally considered adults either because they have reached the age of maturity for their country or because local legislation allows for the classification of pregnant and/or married women as adults.

If children are included in the study, how you will obtain permission for them to participate from their parent, legal guardian, or other legal authority (if child is in foster care or under government supervision) :

All enrolled participants will be consented as adults using the recruitment and consent materials outlined in the sections above.

f. If you are seeking a waiver of informed consent or assent, the justification for this request:

N/A

Whether you will include a witness to the consent process and why: **N/A**

If the language is unwritten, explain how you will communicate accurate information to potential participants and whether you will use props or audio materials: **N/A**

2. Identify the countries where the research will take place, and the languages that will be used for the consent process.

Country	Consent Document(s) (Adult Consent, Parental Permission, Youth Assent, etc.)	Languages
Indonesia	Adult Consent	Bahasa
Kenya	Adult Consent	English, Swahili

C. **Study Implementation:**

1. Describe the procedures that participants will undergo. If complex, insert a table below to help the reviewer navigate.

Key Informant interviews: KIIs will take place at 2 timepoints in the study: baseline and endline. The interviews will be conducted using the semi-structured guide led by a senior study staff member or the PI in a quiet private place. They are expected to last about 90 minutes. KIIs will be conducted in the language of choice of the respondent as data collection tools will be translated into the local dialects specific to the region of study. The interview will be audio recorded and during the interview, the participants will not be addressed by their names. Unique study codes will be assigned to each participant on the interview forms and participant names will not be recorded. At the end of the interview, the data will be analyzed and a summary report will be prepared. The participants may be reimbursed for travel costs/time.

Client Interviews, Focus Group Discussions, and In-Depth Interviews

Client Interviews: Clients opting to participate in this study will be contacted two to three times for the interviewer-administered survey

As displayed in **Table 1** and **Figure 1**, the point of recruitment or entry into the study will differ by country and type of client.

[figure not shown]

Figure 1: Client Participation timepoints

For Postpartum Women

ANC: In Kenya, the first contact for pregnant/postpartum participants, will take place at the participant's ANC visit. At this time, a 30 minute questionnaire will be administered which includes sociodemographic information, assessment of the quality of the client provider knowledge attitudes and beliefs regarding PPFP, and barriers and facilitators of intended PPFP use. The interviewer will also ask to see their ANC card and Mother Child Booklets and note

any pertinent medical or gynecological history that might be relevant to the study – this includes chronic diseases like hypertension, diabetes, HIV and tuberculosis.

Immediate Postpartum: The **first contact for Indonesian postpartum clients** and the **second contact for the Kenyan Postpartum client** will be during the immediate postpartum period, within 72 hours of delivery in Indonesia, within 48 hours of delivery in Kenya. The questionnaire in both countries will be administered to determine whether or not the client received a modern FP method after delivery, how the participant feels about the FP services offered to them during labor and delivery, the participant's knowledge, attitudes and beliefs about PPFP, and reasons for choosing the FP method they chose or for not accepting a FP method at that time. The Kenyan visit will take about 30 minutes while the Indonesian visit will take about 45 minutes. In Indonesian, supplementary questions will be used to collect similar information to what was collected during ANC in Kenya. These questions will identify sociodemographic information and assess the client's perceptions of the quality of the provider interaction at ANC. The interviewer will also ask to see their ANC card and Mother Child Booklets and note any pertinent medical or gynecological history that might be relevant to the study.

6 Months Postpartum: The **final contact** for all postpartum participants (contact #3 for Kenya and contact #2 for Indonesia) will be made 6 months postpartum. The 30 minute questionnaire will be administered to understand participants' experience and satisfaction with their PPFP method choice whether or not they did accept an immediate postpartum FP method, any complications encountered, likelihood of discontinuation of the method and if they would refer PPFP methods to others. Prior to the interview, RAs will contact participants to set the interview time and location and to ensure the participant is still able to participate in the final interview.

Focus Group Discussions: Trained qualitative researchers will conduct the FGDs in a quiet and private place. Each FGD will take approximately 90 minutes to complete and will be conducted in the language participants are most comfortable with. The FGD will be audio recorded and during the FGD, the acceptors will not be addressed by their names, rather they will be called as 'Sister' (or in local languages). Each respondent is required to participate in only one FGD/KII throughout the study.

FGDs will occur only at one timepoint during the study: during year 2 of the study, with participants who have participated in client interviews and are between 6 and 12 months postpartum.

For Postabortion Women

Immediate Postabortion: At the **first contact for Kenyan and Indonesian postabortion participants**, the client will be recruited in the immediate postabortion period (within 72 hours in Indonesia, within 48 hours in Kenya postabortion). At this time, a 30 minute questionnaire will be administered which includes sociodemographic information, assessment of the quality of the client provider knowledge attitudes and beliefs regarding PAFP, their postabortion care experiences, knowledge, attitudes and beliefs about FP methods, and reasons for choosing the method they chose or, if they choose not to accept a method, why they made that choice.

6 Months Postabortion: The **final contact** for postabortion participants will be made 6 months postpregnancy. The 30 minute questionnaire will be administered to understand participants' experience and satisfaction with their PPFP method choice whether or not they did accept an immediate postpregnancy FP method, any complications encountered, likelihood of discontinuation of the method and if they would refer PPFP methods to others.

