	Sample Size, assuming 30% attrition, 10% refusal	Design Effect (2.5) and Cluster Size Adjusted Sample Size Per Arm	Sample size per arm (80% Public, 20% Private)	Total per Country (2 arms)
Kenya Public	721	2254	1803	4508
Kenya Private			451	
Indonesia Public	686	2144	1715	4288
Indonesia Private			429	

Table 5: Sample Size Calculations, Postabortion

Study Arm	Base sample size of post-abortion clients (per arm – assuming 50% uptake and 40% continuation at 6-months)	Attrition Adjusted Sample Size per arm (estimating 20% attrition)
Kenya Intervention	194	243
Indonesia Intervention	194	243
Total		486

Separate sample sizes have been calculated for Indonesia and Kenya. Estimates aim to measure a difference in the six-month postpartum acceptance of long-acting reversible and permanent methods (LARC+PMs) by postpartum women seeking services at comparison and intervention facilities. Sample size calculations for both countries are based on a 95% two-sided confidence interval with 80% power. The sample size was calculated in two stages. First, we calculated the sample size for simple random sampling. Next, the sample size was adjusted to take into account a design effect of 2.5 in order to adjust for within-cluster correlation and non-response.

In Indonesia, we used an analysis of PPPF utilization from the 2012 Demographic and Health Survey (DHS) and conversations with the My Choice project team (My Choice is a Bill and Melinda Gates Foundation-supported project currently strengthening family planning services at facilities in Indonesia) to estimate a baseline LARC+PM use of approximately 10% at six months postpartum. In Kenya, we analyzed FP method use among a subset of 3,857 women with a child under one year interviewed during the 2014 Kenya DHS to estimate a LARC+PM use rate of 6% at six months postpartum. Sample sizes were calculated to measure a change from 10% to 15% in Indonesia and from 6% to 10% in Kenya at intervention facilities over the course of the study. We have further estimated a need for 20% of the sample to be recruited from private facilities in order to effectively measure changes in both types of facilities. An overview of the sample size for each country is shown in Table 4. This table displays the required number of post-pregnancy women to be recruited per arm to measure the change in LARC+PM use post-pregnancy from 10% to 15% in Indonesia and from 6% to 10% in Kenya at the end of the study.

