The population of women who will experience postabortion care was calculated differently. Since the current proportion of these women who take up an FP method after PAC has not been reliably determined in the two countries, we have assumed an estimate of 50% (assumption of 50% provides us a high sample size). After six months, we estimate that 40% of them will still be using the method, and thus we need a sample size of 243 women in the intervention group only, per country. This group will be recruited at baseline, and will include an adjustment of 20% to account for loss to follow-up. This sample size is adequate to detect a 10 percentage point change within a 95% two-sided confidence interval at 80% power. The research question for PAC clients is: what percentage of PAC clients who want to use a method of family planning are using a method six months after the premature end of pregnancy? With this question, we hypothesize that 80% who want a method will get a method.

Health Facility Assessments: Prior to implementation of the study, in order to reach adequate sample size, 18 facilities in Kenya (9 intervention and 9 control, which are each split into 5 public and 4 private-for-profit in each arm) and 8 facilities in Indonesia (4 intervention and 4 control, which are each split into 3 public and 1 private-for-profit in each arm) will be purposefully selected in collaboration with respective Ministries of Health.

IV. Participants:

Describe the study participants and the population from which they will be drawn. Specify the inclusion and exclusion criteria. If you plan to include children, note their ages and whether you will include children in foster care. Note if the participants are particularly vulnerable in terms of cognitive limitations, education, legal migration status, incarceration, poverty, or some combination of factors.

Participants will be selected based on their relationship to intervention and control facilities where the PPPF Choices project is being introduced.

Participants in this study fall into two distinct categories: 1) Key Informants, and 2) female clients who participate in Client Interviews, Focus Group Discussions, and In-Depth Interviews.

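### The 80% power stated for the 243 postabortion clients per country belongs to a one-sample, unclustered test and does not hold for the clustered design or address the stated question; separately, half of the postabortion in-depth interviews are placed where no postabortion client is enrolled.

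*Protocol*

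**What the plan says.** Section III.B of the protocol sizes the postabortion cohort separately from the postpartum sample. Table 5 starts from 194 per country, "assuming 50% uptake and 40% continuation at 6-months", and reaches 243 after 20% attrition. The text explains that uptake after postabortion care is not reliably known in either country, so 50% is assumed. The six-month assumption reads: "After six months, we estimate that 40% of them will still be using the method". From these two rates the protocol draws its number: "thus we need a sample size of 243 women in the intervention group only, per country". The power claim follows: "This sample size is adequate to detect a 10 percentage point change within a 95% two-sided confidence interval at 80% power".

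The same paragraph poses this question, with the clock running from the end of pregnancy: "what percentage of PAC clients who want to use a method of family planning are using a method six months after". It also states a hypothesis: "we hypothesize that 80% who want a method will get a method".

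For the postpartum sample, "the sample size was adjusted to take into account a design effect of 2.5 in order to adjust for within-cluster correlation and non-response". No such step appears for postabortion clients. On facilities, section III.B gives 4 intervention facilities for Indonesia, and for Kenya "18 facilities in Kenya (9 intervention and 9 control, which are each split into 5 public and 4 private-for-profit in each arm". Section V.C.5.A gives six intervention sites in Kenya.

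SAP section A describes proportions in pregnant and postpartum women, an intervention-versus-control regression, and a multilevel model for intention and receipt. It names no postabortion estimate or test.

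For the postabortion in-depth interviews, Table 3 allocates 6 + 2 to intervention and 6 + 2 to control facilities in each country. Appendix II also lists them under recruitment at both kinds of site. The inclusion criteria in section IV.A require interviewees to be enrolled postabortion participants already. Table 2 restricts the interviews to women who had intended to get a method. The text of sections III.B, IV and V.C.1 asks only that no method (or no modern method) was received.

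**The concern.** A power statement is tied to a test, a population and a variance. Here the variance assumes independent women, while recruitment is through a handful of facilities. The population is all postabortion clients, while the question is about those who want a method. The reference value of 50% is an assumption about immediate uptake, whereas the 40% is use six months later in the same cohort. A reader who takes the 80% at face value may expect more from the six-month result than 4 to 9 facilities can give.

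The interview conflict is practical. Interviewees must come from the enrolled postabortion cohort, and the plan provides no such cohort in control facilities.

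**Working it through.** **1. The plan's own figure.** Inputs from section III.B and Table 5: p0 = 0.50, p1 = 0.40, two-sided 5%, 80% power.

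n = [1.96 × √(0.50 × 0.50) + 0.8416 × √(0.40 × 0.60)]² / 0.10² = 193.85, so 194. Attrition: 194 / 0.8 = 242.5, so 243. Both match. A two-group comparison of the same rates would need 388 per arm, so this is a single-group formula. It leaves no room for a design effect.

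**2. Clustering under the one-sample reading.** The documents give no ICC for postabortion clients; 0.01 to 0.05 is my assumption. With k equal-sized facilities, DE = 1 + (194/k − 1) × ICC, and power = Φ[(0.10 × √(194/DE) − 1.96 × 0.5) / √0.24].

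| Intervention facilities | Women per facility | DE (ICC 0.01 / 0.05) | Power (ICC 0.01 / 0.05) |
|---|---|---|---|
| 9 (Kenya, III.B) | 21.6 | 1.206 / 2.028 | 72% / 50% |
| 6 (Kenya, V.C.5.A) | 32.3 | 1.313 / 2.567 | 68% / 41% |
| 4 (Indonesia) | 48.5 | 1.475 / 3.375 | 63% / 33% |

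**3. Within-woman (paired) reading.** If the 10 points are a change from immediate uptake to six-month use in the same women, McNemar's test applies. With d the proportion whose status changes, power = Φ[(0.10 × √n − 1.96 × √d) / √(d − 0.01)].

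| Discordance d | n = 194, unclustered | n = 194/2.5 = 77.6 |
|---|---|---|
| 10% | 99.5% | 81% |
| 25% | 80% | 42% |

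The 2.5 is carried over from the postpartum sample as an assumption.

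**4. Precision for the stated question.** Half-width = t(0.975, k − 1) × √[p(1 − p) × DE / n], with DE = 1 + (n/k − 1) × ICC. The documents do not give the share of clients who want a method, so I take n from 97 (half of 194) to 194 (all), p from 0.32 to 0.64 for illustration, and ICC from 0.01 to 0.05.

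| Facilities | t | Smallest (n = 194, ICC 0.01, p = 0.32) | Largest (n = 97, ICC 0.05, p = 0.50) |
|---|---|---|---|
| 9 | 2.306 | 8.5 points | 14.3 points |
| 6 | 2.571 | 9.9 points | 17.3 points |
| 4 | 3.182 | 12.9 points | 23.8 points |

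**5. Interviews.** Table 3's postabortion client cells add to 174 + 69 = 243 in Kenya and 161 + 82 = 243 in Indonesia. That is exactly the number section III.B and Table 5 assign to the intervention group. Nobody is left for control facilities, yet 2 × (6 + 2) = 16 of the 32 interviews are placed there.

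**The case against.** The strongest reply is that the arithmetic is right and that a one-sample test is the natural test for a single group. Both parts stand. A reader might infer a miscalculation or a wrong type of test, and the documents support neither.

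The second reply is that the text follows one cohort from uptake to continued use, which is a paired change. If that change is pure discontinuation, discordance is 10% and power stays at about 81% even with a design effect of 2.5. This also stands, so it would be too strong to say that the cohort is underpowered. But the plan names no paired test and no discordance. The six-month interview (section V.C.1) also covers women who did not accept a method at first, so late starters may raise discordance. At 25% the margin is gone.

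Two further inferences should be resisted.
- The 40% might be read as 40% of acceptors, that is 0.5 × 0.4 = 20% of clients. The gap would then be 30 points and 194 more than enough. The wording is ambiguous, but no power is lost. The exact match to 194 shows that the calculation used one denominator.
- An ICC might be backed out of Table 4. The 2.5 is said to cover non-response as well, and its base is unclear: 721 × 2.5 = 1,802.5, the public-facility figure of 1,803, while 2,254 / 721 = 3.13. No ICC can be read from it safely.

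On the SAP, protocol section II defines post-pregnancy family planning to include the six months after abortion, and multilevel analysis is planned, so clustering is not ignored altogether. Still, that model addresses intention and receipt, and an arm contrast is impossible in a cohort enrolled in one arm.

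On interview eligibility, the text of three sections does not require a prior plan and only the Table 2 row does. That is a wording mismatch. It does not leave staff without a rule.

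**Conclusion.** The power sentence does not hold as written. The 80% is correct for independent women and a fixed 50% reference; any positive ICC lowers it under that reading. The direction is firm, but the size rests on the assumed ICC of 0.01 to 0.05: 72% to 50%, 68% to 41% or 63% to 33% for 9, 6 or 4 facilities. Equal facility sizes and normal quantiles make these figures favourable if anything. Under the paired reading no shortfall is certain. Under either reading, the calculation does not address six-month use among clients who want a method.

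The interview allocation conflict needs no assumption: 8 of 16 interviews per country have no enrolled source population.

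Severity is minor to moderate, because this is a secondary, single-group cohort and the remedy is mainly wording.

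**What to change.** - Replace the power sentence with a precision statement: a single-group estimate of six-month use among postabortion clients who want a method, with a facility-clustered 95% confidence interval using t on (facilities minus 1) degrees of freedom. Name the same estimate in SAP section A.
- State as assumptions, with a range, the ICC, the number of facilities (reconciling 9 with six in Kenya) and the share of clients who want a method. Say whether the 40% is of all clients or of acceptors. On the illustrative inputs above, the half-width is about 9 to 14 points with 9 facilities, 10 to 17 with 6 and 13 to 24 with 4.
- If a within-woman change is intended, name the paired test, its discordance and its design effect instead.
- Place all 16 in-depth interviews per country in intervention facilities, or state how control-area interviewees are enrolled. Correct Table 3, Appendix II and the enrolment text to agree.
- Align the Table 2 eligibility wording with sections III.B, IV and V.C.1.

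The cost is protocol, table and SAP wording and a less favourable stated precision, with no extra postabortion survey participants. Moving the interviews gives up control-area views; keeping them needs an enrolment route in control facilities.

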Facility Audits: Data Analysis: Mapping of facilities will be visually analyzed to provide further understanding of structural issues that may influence perceptions and key behaviors. We will also utilize multi-level data analysis to explore the feasibility of IPPI using STATA. Select data from the client interviews will be combined with key facility level indicators for a multilevel analysis of the factors affecting intention to use and receipt of immediate post-pregnancy family planning methods.

[figure not shown]
Furthermore, triangulation across methods will help to ensure quality of study findings and offer opportunities for deeper insights into the study concepts [12]. Observations will also be collated with qualitative analysis results and used to strengthen themes identified through key informant data. In addition, a team approach to data analysis will be employed where different researchers provide feedback on emerging interpretations and analysis and check developing categories and concepts back against the original data. In this way, an “audit trail” will be used to help ensure trustworthiness of findings and gather input from multiple investigators [12].

5. Answer the following if they are relevant to your study design:

A. If the study has different arms, explain the process for assigning participants (intervention/control, case/control), including the sequence and timing of the assignment.

The study will employ a quasi-experimental mixed-method design; both quantitative and qualitative data will be collected at multiple time points. In coordination with the MOH, we will first identify an “intervention area” and a “control area” at County-level in Kenya and an “intervention area” and a “control area” at District-level in Indonesia. Within the “intervention areas,” we will identify intervention facility sites (six in Kenya and four in Indonesia) and match them with an equal number of control facility sites from the “control areas,” based on a list of predetermined criteria (e.g., service statistics and client demographics).

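### Indonesia's stated 80% power takes no account of having 4 v 4 facilities and rests on an unsplit 2.5 multiplier; on 6 df, 80% is reached only under favourable assumptions the protocol does not state, and one private facility per arm cannot measure private-sector change

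*Protocol*

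**What the plan says.** Protocol III.B (Client Interviews) sizes the postpartum sample on LARC+PM use at six months: 10% v 15% in Indonesia and 6% v 10% in Kenya. "Sample size calculations for both countries are based on a 95% two-sided confidence interval with 80% power". It begins from simple random sampling; then "the sample size was adjusted to take into account a design effect of 2.5 in order to adjust for within-cluster correlation and non-response". No ICC, cluster size or source is given for the 2.5.

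Table 4 has 686 (Indonesia) and 721 (Kenya) in a column headed "Sample Size, assuming 30% attrition, 10% refusal". Next come 2144 and 2254 under "Design Effect (2.5) and Cluster Size Adjusted Sample Size Per Arm". These are split into 1715 public and 429 private for Indonesia, and 1803 and 451 for Kenya. The text presents them as sufficient: "This table displays the required number of post-pregnancy women to be recruited per arm". The private share is justified as "a need for 20% of the sample to be recruited from private facilities in order to effectively measure changes in both types of facilities".

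The facility numbers come later, under Health Facility Assessments: 9 per arm in Kenya (5 public, 4 private) and "8 facilities in Indonesia (4 intervention and 4 control, which are each split into 3 public and 1 private-for-profit in each arm". Section V.C.5.A, on assignment, instead gives "six in Kenya and four in Indonesia) and match them with an equal number of control facility sites", chosen from one intervention area and one control area per country.

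SAP section A compares arms by bivariate and multivariable logistic regression. Sections A and E add a multilevel model. Neither states denominator degrees of freedom or a small-cluster correction.

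**The concern.** A design effect enlarges the variance. It does not allow for having to estimate the between-facility part of that variance from eight facilities. With 4 v 4 there are 6 between-facility degrees of freedom, and the 5% two-sided critical value rises from 1.96 to 2.45. A figure of 80% computed on the normal reference is then too high for a test that keeps its 5% level.

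A second problem lies in the effective sample. The 2.5 does two jobs in unstated proportions, and the column that claims to hold the loss allowance may not hold it.

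Programme impact is a secondary question (Protocol I), but it is the comparison on which the sample is sized. A null Indonesian result would be read against the stated 80%. The protocol also gives measuring change in both sectors as the reason for recruiting one woman in five from private facilities, so a reader will expect a private-sector result.

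**Working it through.** **1. Reproduce the plan's figures.** Pooled normal two-proportion formula, with p̄ the mean of p1 and p2:

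n = [1.96·√(2p̄(1−p̄)) + 0.842·√(p1(1−p1)+p2(1−p2))]² / (p2−p1)²

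- Indonesia, 0.10 v 0.15: 685.6, so 686, as in Table 4.
- Kenya, 0.06 v 0.10: 720.9, so 721, as in Table 4.

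Both match with no loss allowance. With the allowance in the header, 686/(0.7 × 0.9) would be about 1089. The label is wrong.

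**2. Trace the inflation.**

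- 686 × 2.5 = 1715 and 721 × 2.5 = 1802.5, so 1803. These are exactly the public cells.
- 1715/0.8 = 2143.75, so 2144. 1803/0.8 = 2253.75, so 2254.

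The 1/0.8 is therefore most likely the 20% private top-up, but the protocol does not say so. Arithmetic alone cannot exclude a 20% loss allowance, which is what Table 5 uses (194/0.8 = 242.5, so 243).

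**3. Power on a facility-level t reference, Indonesia.** df = 2 × (4−1) = 6. Noncentrality = 0.05/√[(0.10×0.90 + 0.15×0.85)/n_eff], where n_eff is the effective number of women per arm.

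| n_eff | Noncentrality | Normal | t, 6 df |
|---|---|---|---|
| 686 (behind the stated 80%) | 2.81 | 80% | 65% |
| 2144/2.5 = 857.6 (pooled arm) | 3.14 | 88% | 74% |

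80% on 6 df needs n_eff of about 986. Keeping 1.96 instead gives P(|t| > 1.96) = 9.8% on 6 df, so the test would not be at 5%. Beta-binomial simulation of a t test on 4 v 4 facility proportions (40,000 runs) gives 65.3% and 74.3%, or 74.1% for the larger sample with facility sizes 572, 572, 571 and 429. Null rejection is about 5%.

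**4. Take off 30% loss.** 2144 × 0.7 = 1500.8 women per arm, about 375 per facility instead of 536. The clustering part of the 2.5 is unknown, so each reading is shown twice: with the design effect (DE) held, and with the ICC held so that the DE falls as clusters shrink. ICC = (DE−1)/535.

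| What the 2.5 holds | Starting DE | ICC | Power, DE held | Power, ICC held |
|---|---|---|---|---|
| Clustering only | 2.5 | 0.0028 | 59% | 68% (DE 2.05) |
| Clustering and 30% loss | 2.5×0.7 = 1.75 | 0.0014 | 74% | 79.9% (DE about 1.5) |
| Clustering, loss and 10% refusal | 2.5×0.7×0.9 = 1.575 | 0.0011 | 79% | 83% (DE 1.40) |

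**5. Degrees of freedom other than 6.** Sector-stratified (4 df): 57% at 686 and 66% at 858. Four matched pairs (3 df, no variance gain assumed): 48% and 57%.

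**6. Kenya.** Effective 721 gives 75% (9 v 9, 16 df) or 72% (6 v 6, 10 df). Effective 2254/2.5 = 902 gives 84% or 81%. The answer turns on which facility count and which reading apply.

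**7. Private stratum.** Indonesia has 1 v 1, so 0 df between facilities. Even if clustering, df and loss are all ignored, 429 v 429 gives 60%. Kenya, if 4 v 4 holds (451 per arm, 6 df, no loss): 22% at DE 2.5 and 46% with no clustering at all.

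**The case against.** The strongest reply is that the effective sample is itself unknown, so no single power figure belongs to the plan. The protocol says the 2.5 also covers non-response. Taken at its word, with 30% lost and the DE recomputed for smaller clusters, power on 6 df is about 80% to 83%. This stands. A reader might infer that Indonesia has 65% to 74% power as a fact, or that the shortfall is the same however the 2.5 is divided. The documents do not support either. For a given effective sample the split does not matter, but the effective sample depends on it.

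Next, on the top-up reading of the 1/0.8, 686 is the public cell's effective size, so setting it against whole-arm df mixes two things. This also stands in part. The 65% converts the stated 80% to 6 df; it does not forecast the pooled arm, which starts at 74%. The public cell alone (3 v 3, 4 df) would give 57%.

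Third, the SAP plans logistic and multilevel models, not a facility-level t test. True, so the figures are benchmarks. But the SAP names no small-cluster method that would do better, and assignment by whole area with matched facilities makes 6 df the favourable case.

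Last, the protocol states no private-sector hypothesis or power. That limits the point to the stated reason for the 20% share, which one facility per arm cannot deliver. A reader might also infer that Kenya is underpowered overall; the conflicting facility counts do not allow that.

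**Conclusion.** The point holds for Indonesia. The stated 80% omits the facility count. On 6 df the pooled arm gives 74% before any further loss. After 30% loss, power is about 59% to 68% if the 2.5 is all clustering and about 74% to 83% if it already contains the loss, or the loss and refusal. So 80% is reached only when the 2.5 already contains the loss and the design effect also falls as clusters shrink; neither condition is stated. These figures assume facilities that are independent and about equal in size, the 10% v 15% contrast, and a facility-level analysis.

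The Table 4 header on 686 and 721 is wrong whichever reading is taken. The Indonesian private comparison cannot separate programme from facility, whatever the number of women. Kenya's private comparison has no stated power and looks weak if it is 4 v 4. No overall shortfall is asserted for Kenya.

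The implied ICCs in the working (0.0011 to 0.0028) only show what each reading would require. A reader might take one of them as the plan's assumed ICC, but the protocol gives none.

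**What to change.** In Protocol III.B:

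- Correct the Table 4 header on 686 and 721, and say what the 1/0.8 is.
- Separate attrition and refusal from the design effect. State an ICC for six-month LARC+PM use with a sensitivity range, and use DE = 1 + (m−1) × ICC by country, where m is women per facility.
- Reconcile the Kenya facility count (9 or six per arm) with V.C.5.A.
- Restate power, or the detectable difference, by country on a small-cluster reference whose df match the analysis. Note that area-level assignment and matching make facility-level df the favourable case.
- Withdraw the private-sector claim for Indonesia. Report its private arm difference as descriptive and Kenya's as exploratory.

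In SAP sections A and E, add the same small-cluster correction to the arm comparison.

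The cost is wording and a recalculation, with no added sites or women. The stated power will probably be less favourable.
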